6. STUDY OBJECTIVES AND ENDPOINTS

6.1. Primary Objective and Endpoint

The primary objective of the study is to evaluate the long-term safety and tolerability of BIIB067 in participants with ALS and a confirmed SOD1 mutation.

The associated primary endpoint is the incidence of AEs and SAEs.

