7.2. Overall Study Duration and Follow-Up

The overall duration of study participation for a single participant will be up to 368 weeks, which includes an approximately 4-week screening period, up to a 360-week treatment period, and a 4-week follow-up period.

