16.6.2. Methods of Analysis

16.6.2.1. Adverse Events

AEs will be coded using the Medical Dictionary for Regulatory Activities.

The incidence of all AEs, SAEs, deaths (all causes and ALS-related), and AEs leading to discontinuation will be summarized by system organ class and preferred term by treatment group. The incidence rate per person year may also be determined when long-term dosing follow-up is accrued. The AEs level of severity and relationship to study treatment will also be similarly summarized. For the summary of AEs by severity, if a participant has multiple events occurring in the same body system, then the event with the highest severity will be counted. The relationship to study treatment will be classified as related or not related.

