3.3.2.2 Maintenance Dose Period

During the maintenance portion of the study, subjects will receive up to 90 doses of tofersen, approximately every 4 weeks, during visits at Weeks 8, 12, 16, and every 4 weeks thereafter until the last subject enrolled has had the opportunity to have their Week 152 Maintenance Dose Visit.

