4.9.1. Adverse Events

All AEs will be classified using MedDRA version 27.0 or later. All AEs will be listed but only treatment emergent AEs will be summarized, where treatment emergence will be relative to the first dose of study drug. A treatment emergent AE/SAE is defined as any AE/SAE with an onset date and time that is on or after the first dose of study drug or any pre-existing condition that has worsened in severity after the first dose of study drug. In case of missing dates,

- Any AE/SAE with both a missing onset date and resolution date, or any AE/SAE with a missing onset date and a resolution date which is after the first dose of study drug, will be considered treatment emergent.
- If the onset date is available but onset time is missing and the AE onset date is the same as the first dose date the AE will be considered treatment emergent.
- For AEs with a partial start date, the year/month of the event date will be compared to that of the first dose date to determine whether the event is treatment emergent.

The incidence of treatment emergent AEs will be summarized by study group as follows:

- by primary system organ class (SOC) and MedDRA preferred term sorted by decreasing frequency
- by SOC and MedDRA preferred term sorted by alphabetical order
- by MedDRA preferred term
- by SOC

- The most common treatment emergent AEs i.e. occurring in $\geq 5\%$ subjects in any study group will be presented by MedDRA preferred term.
- For Part C subjects only, the most common treatment emergent AEs i.e. occurring in 2 or more subjects in subjects previously on tofersen in 233AS101 compared to subjects who were on placebo will be presented by MedDRA preferred term.
- By maximum CTCAE grade, primary SOC and MedDRA preferred term
- By maximum CTCAE grade and MedDRA preferred term
- AEs with a CTCAE grade ≥ 3 by primary SOC and MedDRA preferred term
- Related AEs by primary SOC and MedDRA preferred term
- SAEs by primary SOC and MedDRA preferred term
- SAEs by MedDRA preferred term
- Related SAEs by primary SOC and MedDRA preferred term
- AEs related to lumbar puncture (as assessed by the investigator) by primary SOC and MedDRA preferred term
- AEs that occurred within 24 hours of dosing by primary SOC and MedDRA preferred term (in case of partial AE start date, if the month and year are available and day is missing, the AE will be included for any dose that occurs in the same month and year as the AE)

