An additional table for hospitalizations will present the number and percentage of subjects in each treatment group with at least one hospitalization, the number of hospitalizations per subject, total number of hospitalization and a descriptive summary for the total cumulative duration of hospitalizations per subject.

Pre-treatment SAEs i.e. those that occurred between screening and first dose are not considered treatment emergent and so will be summarized separately if there is a sufficient number. Pre-treatment AEs should not be collected unless classed as serious. All SAEs will be listed, with an indicator for pre-treatment SAEs. Only treatment emergent AEs will be summarized, unless otherwise specified.

A separate summary will be presented for each confirmed COVID-19 AE and suspected COVID-19 AE. These will be identified as AEs that are recorded with an entry of '(Confirmed)' and '(Suspected)'. As per the guidance, confirmed cases are those confirmed via a diagnostic test and suspected cases are those diagnosed based on typical symptoms, travel/contact history. A listing will also be provided.

Incidence rate tables

Incidence and incidence rate will be provided in incidence rate tables and will be summarized by primary SOC and MedDRA preferred term by study group. Two different kinds of incidence rate tables will be provided. Definitions are provided below:

- 1) Follow-up adjusted incidence rate – defined as the number of subjects who experienced an event divided by the total of entire follow-up time among the subjects in the analysis population. The entire follow-up time for subject is defined as the time from the first dose until the last day (the earliest date of last study day and interim cutoff date) on study. Each subject will be counted only once within each category. A similar table will also be based on total number of events divided by the total of entire follow-up time among the subjects in the

analysis population. This may count a subject more than once within each category of they experienced an event more than once.

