- 2) Exposure-adjusted incidence rate (EAIR) – defined as the number of subjects who experience an event divided by the total exposure adjusted follow-up time among the subjects in the analysis population. The exposure adjusted follow-up time is defined as the time from the first dose until the initial occurrence of the event for those who experienced an event, or from the first dose until the end of follow-up (the last day (the earliest date of last study day and interim cutoff date) on study) for those who did not. Each subject will be counted only once within each category. If the initial occurrence of the event has a partial start date, the following rules will be applied. If only month and year of the AE are available, and the month and year are same as that of the first dose then it will be assumed that the event started on date of first dose. Otherwise it will be assumed that the event started on the first of the month. If only year is available, and the year is same as that of the first dose then it will be assumed that the event started on the date of first dose. Otherwise it will be assumed that it started on the 1st January.

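### SAP 4.9.1 gives every AE rate as one average over up to 360 weeks of treatment, with no table by time on drug, so a late-emerging or fading risk cannot be read from the planned output

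*SAP*

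**What the plan says.** The primary objective is to "evaluate the long-term safety and tolerability of BIIB067 in participants with ALS and a confirmed SOD1 mutation", and the endpoint is the incidence of AEs and SAEs (Protocol 6.1). On duration, Protocol 7.2 states: "The overall duration of study participation for a single participant will be up to 368 weeks". This includes "up to a 360-week treatment period, and a 4-week follow-up period". Maintenance dosing runs "until the last subject enrolled has had the opportunity to have their Week 152 Maintenance Dose Visit" (SAP 3.3.2.2), so late entrants have much less planned follow-up than early ones.

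SAP 4.9.1 opens its list of tables with "The incidence of treatment emergent AEs will be summarized by study group as follows". The list covers system organ class, preferred term, grade, relatedness, seriousness and similar cuts. The columns (SAP Table 6) are Part C prior placebo, Part C prior tofersen, Parts A+B, and Total. The incidence rate tables then define three rates, all counted from the first 233AS102 dose:

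- **Subject-based follow-up adjusted rate:** "the number of subjects who experienced an event divided by the total of entire follow-up time among the subjects in the analysis population". Time after the event stays in the denominator.
- **Event-based follow-up adjusted rate:** all events over the same denominator.
- **EAIR:** "the number of subjects who experience an event divided by the total exposure adjusted follow-up time among the subjects in the analysis population". Time stops at the first event.

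The AEs-of-note table (serious neurologic events, falls, CSF laboratory abnormalities) specifies only the two follow-up adjusted rates.

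The one AE table about timing concerns events within 24 hours of a dose. By contrast, time on study is shown in 12-week bands (SAP 4.6), and laboratory values and vital signs are shown by visit (SAP 4.9.2, 4.9.3). The protocol commits to little on rates: "The incidence rate per person year may also be determined when long-term dosing follow-up is accrued" (Protocol 16.6.2.1).

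**The concern.** An extension study is where a risk that grows with cumulative exposure, or one that settles after the first doses, should become visible. A single average from first dose to last contact shows neither. A rising risk is diluted by early low-risk time, and an early cluster is diluted by later quiet time.

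The columns also need not have equal follow-up. Part C participants began entering only at protocol Version 4 (SAP 2.3), while Parts A and B could enter earlier. The two Part C columns should have similar calendar opportunity, but one has about 6 months of prior tofersen (SAP 1), which a clock starting at the first 233AS102 dose ignores.

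The documents give some reason not to assume a constant hazard. Dosing is by repeated lumbar puncture, and the SAP plans separate tables for puncture-related events. The intrathecal NOAEL in monkeys was 35 mg at 13 weeks and 12 mg at 9 months (Protocol 5.3.1.1). The latter rests on one animal whose signs began after its second dose, with tremors in the last months of dosing. That proves little about humans, but it makes time-dependence a fair question.

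**Working it through.** **Inputs from the documents.**
- Participation: 4 + 360 + 4 = 368 weeks, which reproduces the protocol's figure. 368 × 7/365.25 = 7.05 years.
- Longest treatment: 360 × 7/365.25 = 6.90 years.
- Last participant enrolled: Week 152 plus the final visit 4 weeks later is 156 weeks; 156 × 7/365.25 = 2.99 years.

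The documents give no follow-up by column. I use 2.99 and 6.90 years as the two ends of the planned range, so the contrast is extreme by construction. Counting the last 4 weeks for the long end as well (364 weeks, 6.98 years) moves the ratios below by about 0.01.

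**Assumed.** All hazards. Both columns always have the same hazard, so a fair comparison has ratio 1.00.

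**Formulas.** With hazard h(t), cumulative hazard H(t), and follow-up T without dropout:
- Subject-based rate = [1 − exp(−H(T))] / T
- EAIR = [1 − exp(−H(T))] / ∫₀ᵀ exp(−H(t)) dt

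**Constant hazard.** The EAIR reduces to h whatever T is, so its ratio is 1.00. The event-based rate also has ratio 1.00. The subject-based rate does not. At 0.1 per year it is 0.258/2.99 = 0.086 against 0.498/6.90 = 0.072.

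| Constant hazard per year | Subject-based rate, 2.99 y | 6.90 y | Ratio | EAIR ratio |
|---|---|---|---|---|
| 0.1 | 0.086 | 0.072 | 0.84 | 1.00 |
| 0.5 | 0.259 | 0.140 | 0.54 | 1.00 |
| 1.0 | 0.318 | 0.145 | 0.46 | 1.00 |

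**Hazard that changes with time.** Example: 1.0 per year for half a year, then 0.1. In the short column 0.527 of subjects have the event over 1.730 mean years at risk, so the EAIR is 0.305. In the long column it is 0.680/3.260 = 0.209.

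| Assumed hazard per year | EAIR, 2.99 y | EAIR, 6.90 y | Ratio, no loss | Ratio, loss 0.15/yr |
|---|---|---|---|---|
| 1.0 for 0.5 y, then 0.1 | 0.305 | 0.209 | 0.68 | 0.76 |
| 0.6 for 0.5 y, then 0.2 | 0.292 | 0.256 | 0.88 | 0.90 |
| 0.05 for 2 y, then 0.2 | 0.095 | 0.140 | 1.47 | 1.40 |
| 0.05 for 3 y, then 0.3 | 0.050 | 0.154 | 3.08 | 2.54 |

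The last column assumes loss independent of the event, which shortens mean follow-up to 2.41 and 4.30 years. The 3.08 is large because the rise comes just after the short column ends.

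**What intervals would show.** In the third row, the pooled long-column figure of 0.140 matches neither true level. Split by time since first dose, the rate is 0.05 in every interval to Week 96 and 0.2 in every interval after Week 144; only the interval containing the change (2 × 365.25/7 = 104 weeks) mixes them. Wherever the hazard is constant within an interval, two columns with the same risk have an interval ratio of 1.00, whatever their total follow-up.

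**The case against.** Several points on the other side stand.

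A reader might infer that the primary question goes unanswered. The documents do not support that: the endpoint as written is AE and SAE incidence, and SAP 4.9.1 reports it. What is missing is its time course, and no current text promises one.

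A reader might also infer that the EAIR generally shows false differences between columns. It does not: at a constant hazard its ratio is 1.00.

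More striking illustrations are possible. If 30% of subjects had the event in the first 4 weeks and none did later, the EAIR would be 14.6 per 100 person-years at 152 weeks and 6.2 at 360, a 2.4-fold gap. That needs no dropout, zero later risk despite lumbar puncture every 4 weeks, and columns at the two extremes. SAP 1 reports many discontinuations among Parts A and B subjects, so the gap should not be taken as an estimate.

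No test between columns is planned, and the explicit AE comparison is within Part C, where follow-up opportunity should be similar.

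Two objections carry less weight. Separate integrated SAPs exist and may contain interval analyses, and Protocol 16.1 mentions integrated safety plans. But this SAP says its standalone analyses focus on safety and exposure, and it expressly defers only efficacy, PD and biomarker endpoints. Second, AEs are listed with dose at onset, and CSF white cell counts are plotted over time for subjects with a value above 10. These help case review, but listings give no person-time at risk and hence no rate.

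**Conclusion.** The point holds as a gap in presentation that is cheap to close. Three things follow from the text alone: each AE rate is a single average from the first 233AS102 dose, treatment can last 360 weeks, and no AE table is by time on drug. A late-emerging or fading risk therefore cannot be read from the planned tables.

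The numerical size is conditional. EAIR ratios of about 0.7 to 0.9 (front-loaded) and 1.5 to 3.1 (late-rising), or about 0.76 to 0.90 and 1.4 to 2.5 with loss of 0.15 per year, rest on assumed hazards and on the ends of the planned follow-up range.

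The weakness of the subject-based follow-up adjusted rate needs no time-varying hazard, only unequal follow-up: ratios of 0.84, 0.54 and 0.46 at 0.1, 0.5 and 1.0 per year without dropout, and 0.88, 0.65 and 0.58 with loss of 0.15 per year. It matters most in the AEs-of-note table, where no EAIR is specified beside it.

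**What to change.** In SAP 4.9.1:

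1. For all treatment-emergent AEs, SAEs, grade 3 or higher AEs and AEs of note, add first-event rates by interval since the first 233AS102 dose, by study group, showing events and person-years at risk. Intervals could be 0–4, >4–24, >24–48, >48–96, >96–144, >144–240 and >240 weeks.
2. For Part C prior-tofersen subjects, also show their 233AS102 events and person-time by time since first tofersen dose, with entry to the risk set at the first 233AS102 dose. Do not use that clock for Parts A+B: SAP 1 reports washouts from 16 weeks to over 2 years, so it would count long off-drug periods.
3. Add the EAIR to the AEs-of-note table.
4. State that the subject-based follow-up adjusted rate is not comparable across columns with unequal follow-up.
5. Base statements about long-term risk on the interval rates.

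The cost is SAP wording and a few more tables. The dates needed are already collected; the parent study's first-dose dates are used only for item 2. Late intervals will hold few subjects and their rates will be imprecise, which the person-years will make plain.

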4.9.2. Laboratory Data

Laboratory data will be evaluated to determine the incidence of abnormalities that emerge during the course of the study. Changes in laboratory evaluations will be presented relative to baseline, which is defined as the closest visit prior to the subject starting treatment.

The following clinical laboratory parameters are assessed in the protocol:

- Hematology panel: complete blood count with differential and platelet count (hematocrit, hemoglobin, platelets, red blood cell count [RBC], white blood cell count [WBC], basophils, eosinophils, lymphocytes, monocytes, neutrophils)
- Blood chemistry panel: albumin, total bilirubin, direct bilirubin, alkaline phosphatase, alanine aminotransferase (ALT) (SGPT), aspartate aminotransferase (AST) (SGOT), gamma-glutamyl transferase (GGT), sodium, potassium, calcium, chloride, phosphate, blood urea nitrogen (BUN), creatinine, uric acid, bicarbonate (CO₂), glucose, total protein.
- Urinalysis: blood, glucose, protein, and microscopic examination if abnormal
- CSF analysis: RBC, WBC, protein, glucose.
- Coagulation: PT (prothrombin time), aPTT (activated partial thromboplastin time), and INR (international normalized ratio).

If multiple samples are collected at the same visit, the samples collected at the earliest date/time will be analyzed after applying visit window rules. For CSF laboratory parameters, tube 2 results will be analyzed if available.

Baseline value is defined as data collected which are prior to and/or on the date of the first dose, usually also the same day as the Day 1 visit. If there is more than one value on or before Day 1, then the last non-missing value prior to (including on) the date of first dose will be used as the baseline value.

Each hematology, blood chemistry, coagulation and CSF laboratory parameter will be flagged as “low” or “high” relative to the parameter’s normal range or as “unknown” if no result is available. For each urinalysis laboratory parameter, the number and percentage of subjects experiencing post-dosing shifts to abnormal will be summarized. For each hematology, blood chemistry, coagulation and CSF parameter, the number and percentage of subjects experiencing post-dosing shifts to ‘low’ or ‘high’ will be summarized. In each summary, the denominator for the percentage is the number of subjects at risk for the shift. The number at risk for the shift to low is the number of subjects whose baseline value was not low and who had at least one post-baseline value. The number at risk for the shift to high is the number of subjects whose baseline value was not high and who had at least one post-baseline value. Subjects will be counted only once for each parameter and each shift regardless of how many post-dosing assessments had that type of shift. Subjects with shift will be listed by laboratory parameter and shift type. All postbaseline data will be used in the shift tables, regardless of whether a scheduled or unscheduled visit. For CSF laboratory parameters, both tubes will be used in this assessment for the shift tables.

Summary statistics for actual values and change from baseline in laboratory values will be summarized by dose group and visit. Line plots for chemistry, hematology and CSF showing mean value for each dose group at each visit will also be presented.

To evaluate potential serious hepatotoxicity subjects with a post-baseline AST and/or ALT value ≥ 3 times the upper limit of normal (ULN) and a post-baseline bilirubin value >2 times ULN at any time, not necessarily concurrent, will be listed with their values. In addition, a plot will be presented with each subject’s maximum post-baseline AST or ALT value relative to the ULN against the subject’s maximum post-baseline bilirubin value relative to the ULN; values do not have to be concurrent. All postbaseline data will be used in the shift tables, regardless of whether a scheduled or unscheduled visit.

Listings of all chemistry, hematology, coagulation, CSF, urinalysis values and pregnancy test (serum and urine) will be provided. Abnormal values and potentially clinically significant values will be flagged.

Subjects with at least one post-baseline CSF WBC values >10 will have their CSF WBC plotted over time in a spaghetti plot. Corresponding listing will also be presented with AEs that occurred at any time on or after the subject had a post-baseline CSF WBC value >10 . A summary table will also present number and percentage of subjects with at least one post-baseline CSF leukocyte >5 and number and percentage with at least one post-baseline CSF leukocyte >10 . The summary will also present total number and percentage of individual values >5 and total number and percentage of individual values >10 . All postbaseline data will be used in the shift tables, regardless of whether a scheduled or unscheduled visit.

A summary table and listing of lumbar puncture and CSF sample collection data other than CSF laboratory results (i.e. lumbar puncture position, number of attempts, interspaces, additional guidance used, CSF volume collected, needle and gauge information) will also be provided.

4.9.3. Vital Signs

Summary statistics for actual values and change from baseline will be presented for each vital sign parameter (temperature, pulse, respiration, systolic and diastolic blood pressure) by dose group and visit. Weight will be summarized at baseline and the last visit by dose group. A listing of vital sign data will also be provided.

Vital signs (temperature, pulse, systolic and diastolic blood pressure) will also be examined to determine the incidence of potentially clinically relevant abnormalities. The number of subjects evaluated and the number of subjects with potentially clinically relevant abnormalities will be presented. All postbaseline data will be used to identify abnormalities, regardless of whether a scheduled or unscheduled visit. The criteria for potentially clinically relevant post-dosing abnormalities are shown in **Table 7** below:

Table 7: Criteria to determine potentially clinically relevant abnormalities in vital signs

Vital Sign	Criteria for Abnormalities
Temperature	<36°C >38°C
Pulse	>100 beats per minute (bpm) <60 bpm
Systolic Blood Pressure	<90 mmHg >140 mmHg >160 mmHg
Diastolic Blood Pressure	<50 mmHg >90 mmHg >100 mmHg
Weight	7% or more increase from baseline 7% or more decrease from baseline
Respiratory Rate	<12 >20

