16.6.2.3. Vital Signs

Changes from baseline will be summarized for all vital signs by visit. A separate summary will be presented for incidence of clinically significant changes from baseline.

CONFIDENTIAL

The information contained herein may not be used, disclosed, or published without the written consent of
Biogen MA Inc.

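### Vital-sign abnormalities other than weight are counted without regard to baseline status, so the table does not give the incidence of change from baseline that the protocol promises

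*SAP*

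**What the plan says.** Protocol 16.6.2.3 asks for two vital-sign summaries. The first is by visit: "Changes from baseline will be summarized for all vital signs by visit". The second is distinct: "A separate summary will be presented for incidence of clinically significant changes from baseline".

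SAP 4.9.3 keeps the first, giving actual values and change from baseline by visit. For the second it refers to Table 7: "The criteria for potentially clinically relevant post-dosing abnormalities are shown in" that table. Temperature, pulse, systolic and diastolic pressure and respiratory rate have fixed cut-offs. Only weight is judged against baseline, for example "7% or more increase from baseline". The counting rule is: "All postbaseline data will be used to identify abnormalities, regardless of whether a scheduled or unscheduled visit". The output is: "The number of subjects evaluated and the number of subjects with potentially clinically relevant abnormalities will be presented". The SAP does not define who counts as evaluated. Percentages are not mentioned in 4.9.3 and follow only from the general rule for categorical endpoints in SAP 4.1.

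For laboratory shifts, SAP 4.9.2 does condition on baseline: "In each summary, the denominator for the percentage is the number of subjects at risk for the shift". It spells this out: "The number at risk for the shift to high is the number of subjects whose baseline value was not high", with at least one post-baseline value also required.

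SAP Section 5 lists the departures from the protocol's planned analyses. The vital-sign rule is not among them.

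**The concern.** SAP 4.9.3 describes its output as an incidence of post-dosing abnormalities. A subject with systolic pressure above 140 mmHg or pulse below 60 bpm before the first dose, and again at any later reading, enters that count although nothing has changed. The table then mixes pre-existing and emergent findings, and a reader cannot separate them.

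SAP Section 1 says the standalone report will focus on safety and exposure, so this separation is part of what the report is for.

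There is a second, separate issue. A count of subjects with at least one reading beyond a limit grows with the number of readings. The Table 6 study groups may differ in that number:
- Follow-up length varies with enrolment date.
- SAP Section 1 reports a large proportion of discontinuations among Part A and B subjects.
- SAP 2.3 and 3.1 show that post-dose vital signs were added only at protocol version 4.0, when Part C subjects began to enrol.

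**Working it through.** The plan states no figure for vital-sign abnormalities, so there is none to reproduce.

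**1. Baseline conditioning across the SAP's safety analyses**

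| Analysis | Baseline condition? |
|---|---|
| Adverse events (4.9.1) | Yes: onset after first dose, or worsening |
| Laboratory shifts (4.9.2) | Yes: at-risk denominator |
| CSF leukocytes >5, >10 (4.9.2) | No |
| Vital signs, Table 7 weight (4.9.3) | Yes: relative to baseline |
| Vital signs, Table 7 other rows (4.9.3) | **No** |
| ECG categories (4.9.4) | Yes: shift from normal |
| QTcF increases >30 to 60 and >60 ms (4.9.4) | Yes: relative to baseline |
| QTcF >480 to 500 and >500 ms (4.9.4) | No |
| Treatment-emergent suicidal behaviour (4.9.7) | Yes: none at baseline |

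**2. Scheduled post-baseline readings per subject**

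The Schedule of Activities has pre-dose and post-dose vital signs at dosing visits. The count is Day 1 post-dose (1), Days 15 and 29 (2 × 2 = 4), two per maintenance visit, and the final visit (1).
- To Week 152: (152 − 8)/4 + 1 = 37 maintenance visits, so 1 + 4 + 74 + 1 = **80**.
- To Week 360: (360 − 8)/4 + 1 = 89 maintenance visits, so 1 + 4 + 178 + 1 = **184**.

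The 184 is a ceiling. Early Part A and B visits had pre-dose readings only, and discontinuation shortens the series.

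**3. Pre-existing abnormality: an illustration**

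The documents give no vital-sign distribution. Assume systolic pressure has mean 125 mmHg, between-subject SD 12 and within-subject SD 8. A subject whose own mean is 125 + u exceeds limit L at one reading with probability q(u) = P(Z > (L − 125 − u)/8). Then:
- share above L at baseline = E[q]
- share flagged under the SAP rule = E[1 − (1 − q)^n]
- share flagged among those not above L at baseline = E[(1 − q)(1 − (1 − q)^n)] / E[1 − q]

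For L = 140, the share above at baseline is P(Z > 15/√(144 + 64)) = P(Z > 1.04) = 14.9%.

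| Limit | Readings | SAP rule | Not above limit at baseline | Share of those counted who were above at baseline |
|---|---|---|---|---|
| >140 | 80 | 63.7% | 57.5% | 23% |
| >140 | 184 | 70.6% | 65.5% | 21% |
| >160 | 80 | 10.7% | 10.0% | 7% |
| >160 | 184 | 14.3% | 13.7% | 5% |

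The baseline condition removes the pre-existing cases. It leaves most of the growth with number of readings.

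**4. Accumulation over readings**

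Assume a per-reading rate p. If readings are independent, P(at least one) = 1 − (1 − p)^n. With intra-subject correlation ρ, use a beta-binomial with a = p(1 − ρ)/ρ and b = (1 − p)(1 − ρ)/ρ, so that P(at least one) = 1 − B(a, b + n)/B(a, b).

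| p | n | Independent | ρ = 0.1 | ρ = 0.3 |
|---|---|---|---|---|
| 1% | 80 | 55% | 19% | 8.5% |
| 1% | 184 | 84% | 25% | 10% |
| 5% | 80 | 98% | 66% | 36% |
| 5% | 184 | ~100% | 76% | 42% |

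Neither p nor ρ is in the documents. At p = 1% and 184 readings, the answer runs from 84% to about 10% on the choice of ρ alone.

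**The case against.** Four things can fairly be said for the plan.

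- **Absolute thresholds are used elsewhere in this SAP.** The CSF leukocyte counts and the QTcF >480 ms rows also ignore baseline. That shows the style is deliberate in places. It does not deliver the protocol's second vital-sign summary, which is worded as change from baseline.
- **The SAP has not dropped change from baseline.** A reader might infer that it has. It has not: by-visit change is kept, the data are listed, and weight is baseline-relative. The mismatch is confined to the second sentence of Protocol 16.6.2.3.
- **The consequence is limited.** The table is descriptive. The version 3 amendment rationale says clinically significant abnormal values will be captured as adverse events, and SAP 4.9.1 gives adverse events follow-up-adjusted and exposure-adjusted rates. This stands, and it is why the point is minor.
- **The laboratory shift tables also accumulate over follow-up**, despite their at-risk denominator. This stands too: accumulation is a separate matter and needs its own remedy.

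A reader might also infer that, over years of readings, chance alone would flag nearly every subject. The documents do not support this. It needs assumed rates and near-independent readings within a person. It fails with moderate correlation and for rarer limits such as systolic pressure above 160 mmHg.

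**Conclusion.** The point holds. For every Table 7 row except weight, a subject already beyond the limit at baseline is counted as a post-dosing abnormality. That is not the incidence of clinically significant change that Protocol 16.6.2.3 promises, it differs from the SAP's own laboratory rule, and Section 5 does not declare it.

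How many subjects this affects cannot be derived from the documents. The 21% to 23% for systolic pressure above 140 mmHg rests wholly on the assumed mean and SDs; for the rarer 160 mmHg limit the same assumptions give 5% to 7%. The dependence on follow-up is real in direction, but its size is equally open.

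Severity is low. No test, alpha or sample size is affected, and the change is worth making because it is cheap.

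**What to change.** In SAP 4.9.3:

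1. For each absolute Table 7 criterion, define the denominator as subjects who do not meet it at baseline and have at least one post-baseline value. List the subjects who met it at baseline. This also settles who counts as evaluated.
2. Separately, give the number and percentage of individual readings meeting each criterion, as 4.9.2 does for CSF leukocytes, or a follow-up-adjusted rate as in 4.9.1. The first change alone does not remove the dependence on follow-up, and reading-level percentages do not make the subject-level percentages comparable. They supply a measure that does not rise automatically with the number of readings.
3. If the present rule is kept, declare it in Section 5 as a departure from Protocol 16.6.2.3.
4. Reconcile the text of 4.9.3, which names temperature, pulse and blood pressure for this analysis, with Table 7, which also has weight and respiratory rate.

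The cost is SAP wording, one denominator rule and an added column or listing; no new data are needed. The downside is that subjects abnormal at baseline leave the row concerned, so any worsening in them shows only in the listing and the by-visit changes.
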